#### 4.0 Test Schedule

##### 4.1 Test schedule Phase I and II

Tests and Procedures	Prior to Registration		Active Monitoring Phase			
	≤28 days prior to registration	≤14 days prior to registration	Every 14 days during 1 st 2 cycles a	Cycles 1-24: Every 28 days (Day 1 of every cycle) pre-treatment a,b	Cycles 25 and after: Every 84 days (Day 1 of every cycle) pre-treatment a,b	End of treatment a
Informed Consent	X					
Complete medical and disease history		X	X	X	X	X
Physical examination including skin exam c	X	X		X	X	X
Height	X					
Vital signs c		X	X	X	X	X
Performance status (ECOG scale)(Appendix IV)	X			X	X	X
Registered in the REVOLIMID REMSTM program o	X			X	X	
Hematology d		X	X	X	X	X
Coagulation e		X		X	X	
Blood chemistries f		X	X	X	X	X
Bone marrow aspirate and biopsy with standard clinical testing (including but not limited to myeloma FISH and flow cytometry)	X			X g	X g	X g
Electrophoresis of serum and urine (SPEP/UPEP)	X			X	X	X
Affected immunoglobulin	X			X r	X r	X r
Immunofixation serum and urine (IF)	X			X	X	X
Immunoglobulin free light chain (FLC)	X			X	X	X
Serum β2-microglobulin, CRP		X				
ECG p		X		X p	X p	
Skeletal bone survey	X			X h	X h	X h
PET scan	X			X h	X h	X h
Research blood sample (Section 14.0) R		X q		X	X	X
Research bone marrow (Section 14.0) i,R	X q			X	X	X
Concomitant medications j		X				
Adverse Event monitoring k		X	X	X	X	X
Pregnancy test l		X		X	X	X
Patient Medication Diary (Appendix VIII) m				X	X	X

Tests and Procedures	Prior to Registration		Active Monitoring Phase			
	≤28 days prior to registration	≤14 days prior to registration	Every 14 days during 1 st 2 cycles a	Cycles 1-24: Every 28 days (Day 1 of every cycle) pre-treatment a,b	Cycles 25 and after: Every 84 days (Day 1 of every cycle) pre-treatment a,b	End of treatment a
Patient Questionnaire Booklets, (Appendix IX) n		X		X	X	X

Cycle length = 28 days Cycles 1-24; Cycle length = 84 days Cycles 25 and beyond

- a) All scheduled visits will have a window of  $\pm 3$  days unless otherwise stated, all procedures to be completed  $\leq 3$  days prior to commencing subsequent treatment cycle
- b) Does not need to be repeated on Cycle 1, Day 1, if completed  $\leq 14$  days prior to registration
- c) To include blood pressure, pulse rate, temperature, weight. Screening for second primary malignancies and especially dermatologic cancers is recommended per standard clinical practice. All patients must have documentation at baseline for any skin lesions considered at risk of a melanoma or non-melanomatous skin cancer. If any such lesion is identified, it should be addressed immediately. During the conduct of the clinical trial, please monitor for any potential skin malignancy lesions, as considered clinically necessary. All male patients at risk for prostate cancer recommended to undergo screening including a serum PSA level if not done  $\leq 6$  months prior to registration.
- d) Hematology: CBC with differential, including hemoglobin and platelet count
- e) Coagulation: prothrombin time (PT) and international normalized ratio (INR)
- f) Blood chemistries: sodium, chloride, potassium, magnesium, phosphate, uric acid, BUN, glucose, ALT/AST (SGPT/SGOT), alkaline phosphatase, total protein, total bilirubin, albumin, serum creatinine, and estimated creatinine clearance (Appendix V), calcium and lactate dehydrogenase (LDH).
- g) Standard of care procedure  $\leq 28$  days prior to registration, and to document CR, sCR or PD while on treatment (whether PD noted to single-agent ibr or the combination of ibr with len+dex). **NOTE:** For Phase II, an additional bone marrow biopsy and aspirate will be collected after completion of Cycle 1 of treatment for correlative sample collection in order to evaluate the exploratory endpoints of the study.
- h) Skeletal bone survey and PET scan for extramedullary disease assessment  $\leq 28$  days prior to registration and then at any time when disease progression is noted, clinically or on laboratory assessment.
- i) Per Section 14, to coincide with the timing of all standard-of-care bone marrow aspirate/biopsy collections in addition to a mandatory collection done prior to starting second cycle in Phase 2.
- j) Concomitant medications: all on-going medications and those taken  $\leq 14$  days prior to first dose until 30 days after the last dose. Recorded in medical record only after baseline. Prior to every cycle, all patient medications must be reviewed and recorded in the medical record (see Appendix X for a list of contraindicated medications).
- k) During treatment period, at end of treatment visit. The patient should be contacted by a nurse 30 days after the last dose of study treatment (or at the time of initiation of subsequent treatment if started before 30 days) to check if the patient has experienced any late adverse events. Grade 3 or higher adverse events at least possibly related to study treatment and deaths due to any cause should be reported as a late adverse event on the event monitoring form if they were not already reported on the Adverse Event form for the last cycle and they occurred prior to any subsequent treatment. and 30 days post-end of treatment

- l) For persons of childbearing potential, a negative pregnancy test (urine or serum) must be documented. A person of childbearing potential is a sexually mature human with an intact uterus who: 1) has not undergone a hysterectomy or bilateral oophorectomy; or 2) has not been naturally postmenopausal for at least 24 consecutive months (i.e., has had menses at any time in the preceding 24 consecutive months). Frequency of testing as required by REMS® program or as clinically indicated.
- m) To be collected on day 1 of every cycle starting cycle 2 and at end of treatment, in order to document patient compliance to treatment. Separate records to be collected for ibrutinib, lenalidomide and dexamethasone
- n) MDASI-MM questionnaire to be completed at baseline ( $\leq 14$  days prior to starting treatment), at the end of Cycle 1 ( $\pm 3$  days), at the end of Cycle 6 ( $\pm 3$  days) and at completion of Cycle 12 of treatment ( $\pm 3$  days), at any time the patient progresses while on the 3-drug regimen and is removed from the study treatment ( $\leq 14$  days after removal from the study)
- o) All unused lenalidomide must be returned as instructed through the REVOLIMID REMSTM program.
- p) To be performed at screening and as clinically indicated throughout the study. Check ECG at any time if the patient's vital signs suggest an issue or if the patient has complaints that could be related to atrial fibrillation including subtle findings such as otherwise unexplained fatigue or nausea.
- q) Collected after registration but prior to treatment.
- r) Serum immunoglobulins to include IgA, IgG, IgM in all cases and IgD, IgE as clinically indicated.

R Research test (see [Sections 14.0 and 19.0](#)).

#### 4.2 Event Monitoring/Survival Follow-up

		Event Monitoring Phase 			
	q. 3 months until PD or subsequent treatment	At PD or subsequent therapy	After PD or subsequent therapy q. 6 months	Death	New Primary
Event Monitoring	X	X	X	X	At each occurrence

1. If a patient is still alive 3 years after registration, no further follow-up is required.

**5.0 Grouping Factor:**

## 5.1 Phase I vs. Phase II

**6.0 Registration/Randomization Procedures**

## 6.1 Phase I

**Prior to discussing protocol entry with the patient, call the MCCC Registration Office [contact]) for dose level and to insure that a place on the protocol is open to the patient.**

## 6.11 Registration Procedures

6.111 To register a patient, [contact]) a completed eligibility checklist to the Mayo Clinic Cancer Center (MCCC) Registration Office between 8 a.m. and 4:30 p.m. central time Monday through Friday.

## 6.2 Phase II

## 6.21 Registration Procedures

6.211 To register a patient, access the Mayo Clinic Cancer Center (MCCC) web page and enter the registration/randomization application. The registration/randomization application is available 24 hours a day, 7 days a week. Back up and/or system support contact information is available on the Web site. If unable to access the Web site, call the MCCC Registration Office at [contact] between the hours of 8 a.m. and 4:30 p.m. Central Time (Monday through Friday).

The instructions for the registration/randomization application are available on the MCCC web page (<http://ccswww.mayo.edu/training/>) and detail the process for completing and confirming patient registration. Prior to initiation of protocol treatment, this process must be completed in its entirety and a MCCC subject ID number must be available as noted in the instructions. It is the responsibility of the individual and institution registering the patient to confirm the process has been successfully completed prior to release of the study agent. Patient registration via the registration/randomization application can be confirmed in any of the following ways:

- Contact the MCCC Registration Office [contact]. If the patient was fully registered, the MCCC Registration Office staff can access the information from the centralized database and confirm the registration.
- Refer to “Instructions for Remote Registration” in section “Finding/Displaying Information about A Registered Subject.”

## 6.3 Phase I and II

## 6.31 Correlative Research:

A mandatory correlative research component is part of this study, the patient will be automatically registered onto this component (see Sections 3.19e and 14.1).

6.32 Prior to accepting the registration, registration/randomization application will verify the following:

- IRB approval at the registering institution

- Patient eligibility
- Existence of a signed consent form
- Existence of a signed authorization for use and disclosure of protected health information

6.33 Documentation of IRB approval must be on file in the Registration Office before an investigator may register any patients.

In addition to submitting initial IRB approval documents, ongoing IRB approval documentation must be on file (no less than annually) at the Registration Office ([contact]). If the necessary documentation is not submitted in advance of attempting patient registration, the registration will not be accepted and the patient may not be enrolled in the protocol until the situation is resolved.

When the study has been permanently closed to patient enrollment, submission of annual IRB approvals to the Registration Office is no longer necessary.

6.34 At the time of registration, the following will be recorded:

- Patient has/had not given permission to store and use his/her sample(s) for future research of multiple myeloma at Mayo.
- Patient has/had not given permission to store and use his/her sample(s) for future research to learn, prevent, or treat other health problems.
- Patient has/had not given permission for MCCC to give his/her sample(s) to researchers at other institutions.

6.35 Treatment on this protocol must commence at Mayo Clinic under the supervision of a medical oncologist/hematologist.

6.36 Treatment cannot begin prior to registration and must begin  $\leq$  28 days after registration.

6.37 Pretreatment tests/procedures (see Section 4.0) must be completed within the guidelines specified on the test schedule.

6.38 All required baseline symptoms (see Section 10.6) must be documented and graded.

6.39a Study drug is available on site.

6.39b Patient questionnaire booklet is available on site; copies are not acceptable for this submission.

## 7.0 Protocol Treatment

### 7.1 Treatment Schedule

#### 7.11 Phase I Treatment Schedule

##### Cycles 1-24

Agent	Dose Level	Route	Day	Cycles
Ibrutinib	As assigned by MCCC Registration Office	PO	1-28	Cycle 1-24
Lenalidomide	25 mg	PO	1-21	Cycle 1-24
Dexamethasone	40 mg*	PO	1, 8, 15, 22	Cycle 1-24

Cycle length = 28 days

\*Starting dose level of dexamethasone for patients  $\geq 75$  years old will be 20mg

##### Cycles 25 and beyond

Agent	Dose Level	Route	Day		Cycles
Lenalidomide	25 mg	PO	1-21	Repeat every 28 days x 3 for each cycle	Cycles 25 and beyond
Dexamethasone	40 mg*	PO	1, 8, 15, 22		

Cycle length = 84 days

\*Starting dose level of dexamethasone for patients  $\geq 75$  years old will be 20mg

Treatment schedule will follow the study schema outlined above. All patients will start with ibrutinib as assigned by the registration office, lenalidomide 25 mg PO days 1-21, and dexamethasone 40 mg PO weekly. **EXCEPTION:** Lenalidomide will be adjusted per guidelines for renal dysfunction with CrCl between 30-60 ml/min (see Table 8.32).

Treatment will be continued until disease progression as long as the patient continues to respond and does not have any unacceptable toxicity. All the patients enrolled in the trial will have a follow up for at least 3 years after registration to capture the secondary endpoints of the study.

Note: Thromboprophylaxis is required as standard of care (see Section 9.3).

#### 7.12 Phase II Treatment Schedule (To be implemented after FDA review of Phase I)

##### Cycles 1-24

Agent	Dose Level	Route	Day	Cycles
Ibrutinib	As determined in Phase I	PO	1-28	Cycle 1 and beyond
Lenalidomide	25 mg	PO	1-21	Cycle 2 and beyond (Not given in Cycle 1)
Dexamethasone	40 mg*	PO	1, 8, 15, 22	Cycle 1 and beyond

Cycle length = 28 days

\*Starting dose level of dexamethasone for patients  $\geq 75$  years old will be 20mg

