##### Cycles 25 and beyond

Agent	Dose Level	Route	Day		Cycles
Lenalidomide	25 mg	PO	1-21	Repeat every 28 days x 3 for each cycle	Cycles 25 and beyond
Dexamethasone	40 mg*	PO	1, 8, 15, 22		

Cycle length = 84 days

\*Starting dose level of dexamethasone for patients  $\geq 75$  years old will be 20mg

Treatment schedule will follow the study schema outlined above. All patients will start with ibrutinib at the dose level determined by the phase I portion and dexamethasone 40 mg PO weekly. Lenalidomide 25 mg PO Days 1-21 will be added Cycle 2.

Treatment will be continued until disease progression as long as the patient continues to respond and does not have any unacceptable toxicity. All the patients enrolled in the trial will have a follow up for at least 3 years after registration to capture the secondary endpoints of the study.

7.2 Treatment by a local medical doctor (LMD) is not allowed.

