**ALERT:** **ADR reporting may be required for some adverse events (See Section 10)**

#### 8.1 General Considerations:

- a) Missed doses are to be omitted rather than made up, unless the dose of one of the study drugs was forgotten and remembered on the same day, in which case the dose can be taken that day. Any doses missed on a particular day are not to be made up the next day.

Doses that are considered to be vomited are not to be made up and a mention about the time of dose and time of vomiting episode should be made in the pill diary.

- b) If multiple toxicities are experienced, dose modifications will be based on the toxicity requiring the largest dose reduction.
- c) Reductions are based on the dose given in the preceding cycle and are based on toxicities with an attribution of possible, probable, or definite that were observed since the prior toxicity evaluation.
- d) If either ibrutinib or lenalidomide must be permanently discontinued, the patient will be removed from the protocol therapy.
- e) If a drug is omitted due to specific adverse events and the patient is on combination therapy, the other agents, considered unrelated to the adverse event may be continued.
- f) A dose omission of >28 days for ibrutinib or lenalidomide is not allowed. If a patient cannot be administered a dose for >28 days due to adverse events or any other reason, the patient should be removed from the study treatment and go to event monitoring.
- g) Patients will be removed from the study if we are unable to manage the adverse events they experience, and it is therefore necessary to permanently discontinue ibrutinib or lenalidomide. These events are listed in the tables in Section 8.3 and 8.5.

8.2 Dose Reductions for Phase I cycles 2 and beyond and Phase II portion (based on Adverse Events in Tables below):

8.21 The following recommended dose modifications will be utilized for ibrutinib, lenalidomide and/or dexamethasone separately as per the best judgment of which drug was most likely to have caused the toxicity:

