**Appendix VIIa                    Patient Medication Diary (Phase I/Phase II)**

(Phase I, all cycles and Phase II Cycle 2 and beyond)

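### The two Phase II treatment tables disagree on whether ibrutinib is part of the regimen from Cycle 25 on

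*Combined protocol and SAP*

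**What the plan says.** Section 7.12 sets out Phase II treatment in two tables. The first is headed for Cycles 1-24, with the note "Cycle length = 28 days". It gives ibrutinib daily and puts "Cycle 1 and beyond" in the cycle column. Dexamethasone carries the same entry, and lenalidomide an equally open-ended one starting at Cycle 2.

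The second table, for "Cycles 25 and beyond", has 84-day cycles. It lists lenalidomide and dexamethasone and has no ibrutinib row.

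The text below it says: "Treatment schedule will follow the study schema outlined above". It then says: "Treatment will be continued until disease progression as long as the patient continues to respond and does not have any unacceptable toxicity". Neither sentence names the agents given after Cycle 24. The Phase II schema survives in this copy only as footnotes and a drug list.

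Section 7.11 (Phase I) also uses two tables, but there the ibrutinib row states a range that closes at Cycle 24, and the later table omits the drug. Phase I therefore agrees with itself.

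Sections 4.2 and 7.12 set follow-up at three years from registration. Sections 2.22 and 2.24 make progression-free survival on the three-drug combination, and duration of response on the same regimen, Phase II secondary objectives.

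**The concern.** An open-ended entry for the study drug in one table and no row for it in the next give a site two instructions for the same patient. One reading continues three drugs past Cycle 24; the other continues two.

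If sites differ, patients who do well enough to stay on treatment would have different ibrutinib exposure late in follow-up for no planned reason. Three things could suffer:

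- **Late safety exposure.** The period at risk on ibrutinib would depend on the reading.
- **Compliance.** Note (m) to the test schedule asks for separate records for each drug. After Cycle 24 it is unclear whether an ibrutinib dose not taken is a missed dose or a dose never scheduled.
- **Late progression-free survival and duration of response.** Events after Cycle 24 could arise under two drugs or three, while the objectives describe a three-drug regimen.

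**Working it through.** **1. The plan's own figures.** The plan states no number for this point. The Phase II operating characteristics in 16.32 are the only design figures that could be in question, so they were reproduced. With 15 patients at the interim analysis (stop at 10 or fewer successes) and 34 in all (26 or more is promising):

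- P(stop) = P(X1 <= 10), X1 ~ Bin(15, p)
- P(promising) = sum over x = 11 to 15 of P(X1 = x) * P(X2 >= 26 - x), X2 ~ Bin(19, p)

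| True rate | Promising: stated | Computed | Stop: stated | Computed |
|---|---|---|---|---|
| 0.65 | 0.092 | 0.0924 | 0.648 | 0.6481 |
| 0.70 | 0.233 | 0.2325 | 0.485 | 0.4845 |
| 0.75 | 0.459 | 0.4585 | 0.314 | 0.3135 |
| 0.80 | 0.715 | 0.7148 | 0.164 | 0.1642 |
| 0.85 | 0.904 | 0.9042 | 0.062 | 0.0617 |

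All agree to the printed precision. None of the inputs refers to treatment after Cycle 24. Response counts at any time over all cycles (16.11), so only a first confirmed response after Cycle 24 could be touched.

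**2. The tables side by side.**

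| Drug and phase | Table for Cycles 1-24 | Table from Cycle 25 |
|---|---|---|
| Ibrutinib, Phase I | range closing at Cycle 24 | no row |
| Ibrutinib, Phase II | "Cycle 1 and beyond" | no row |
| Dexamethasone, Phase II | "Cycle 1 and beyond" | listed |
| Lenalidomide, Phase II | from Cycle 2, no end | listed |

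The second row is the conflict. Open-ended wording goes with continuation for the other two drugs and with absence for ibrutinib.

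**3. When it bites.**

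- First 24 cycles: 24 x 28 = 672 days, so Cycle 25 starts on treatment day 673.
- At 365.25/12 = 30.44 days per month: 672/30.44 = 22.1 months from the start of treatment.
- Treatment may start up to 28 days after registration (6.36): (672 + 28)/30.44 = 23.0 months from registration.
- Three years is 36 months. The time left is 36 - 22.1 = 13.9 months (39%) down to 36 - 23.0 = 13.0 months (36%).

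**4. How many patients.** The documents give no assumption for progression-free survival. For illustration only, assume an exponential distribution with median m, so S(t) = exp(-ln 2 * t/m), with t = 22.1 to 23.0 months and 34 patients. The share of events by month 36 that fall after Cycle 24 is [S(t) - S(36)]/[1 - S(36)].

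| Assumed median (months) | S(t) | Progression-free at Cycle 25, of 34 | Share of events after Cycle 24 |
|---|---|---|---|
| 12 | 0.265-0.279 | 9.0-9.5 | 16-18% |
| 24 | 0.515-0.529 | 17.5-18.0 | 25-27% |
| 36 | 0.642-0.654 | 21.8-22.2 | 28-31% |
| 48 | 0.717-0.727 | 24.4-24.7 | 30-33% |

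The patient counts are upper limits under each assumption, because a progression-free patient may already have left treatment for another reason.

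**5. Related rules.** Section 8.1(f) takes a patient off study treatment when ibrutinib or lenalidomide cannot be given for more than 28 days, whatever the reason. Section 13.3 sends patients to event monitoring for progression on the three-drug combination, and for an ibrutinib or lenalidomide omission running more than 28 days past the scheduled retreatment date. Neither says how it applies if ibrutinib is no longer scheduled.

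**The case against.** The best defence is that the heading over the first table bounds every row in it. The cycle column has to separate drugs that start in Cycle 1 from lenalidomide, which starts in Cycle 2, so the open-ended wording could be only a start marker. The second table would then be the full list from Cycle 25, and it matches the Phase I list. This reading is coherent, but the text does not compel it. The Phase I row under the same heading closes the range explicitly, and the same Phase II wording covers dexamethasone, which does continue.

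The schema may settle the intent. That limits what can be said from this copy, and a figure lost in extraction is not a fault of the plan. It would not remove the disagreement between the tables.

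Four stronger inferences are tempting, and the documents do not support them:

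- **That the diary shows ibrutinib continues.** Appendix VIIIa has an ibrutinib row and is labelled "Phase I, all cycles and Phase II Cycle 2 and beyond". The same form therefore serves Phase I cycles in which no ibrutinib is scheduled, and patients enter zero on days without drug. It is a generic form, not a dosing instruction.
- **That 8.1(d) contradicts a planned stop.** It reads: "If either ibrutinib or lenalidomide must be permanently discontinued, the patient will be removed from the protocol therapy". It stands in the section on dose modification for adverse events, and a scheduled end of dosing is a different event.
- **That late progression-free survival and duration of response do mix two treatments.** This follows only if sites read the tables differently. Treatment must start at the sponsoring institution (6.35) and local physicians may not treat (7.2), which lowers that risk. No passage shows divergence.
- **That the endpoint definitions need a new rule.** Section 16.42 already defines the events for both endpoints and the censoring for progression-free survival. A scheduled change of regimen is neither progression nor subsequent myeloma treatment, so follow-up continues once the schedule is clear.

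**Conclusion.** The concern holds as an internal inconsistency in the Phase II schedule. The two tables in 7.12 do not agree on ibrutinib from Cycle 25, and no readable text resolves it. It applies to every Phase II patient still on treatment after 672 days and covers about 36% to 39% of the three-year follow-up.

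The consequence for late safety exposure, compliance and the late secondary endpoints is a risk, not an established effect. The documents do not give its size. The illustrative 9 to 25 of 34 patients rests wholly on assumed exponential medians of 12 to 48 months.

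The decision rule, sample size, significance level and power stand. The primary analysis is also early: 18 months of accrual plus 6 months of follow-up (16.13, 16.6) is 24 months. At 2 patients per month, only those treated in the first 24 - 22.1 = 1.9 months, about 4, could have reached Cycle 25 by then. The correction is worth making because it concerns what patients receive. Nothing here says which schedule is right.

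**What to change.** Reconcile the two Phase II tables in 7.12 with each other and with the Phase II schema, so that one statement names the agents given from Cycle 25 on.

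Then check that two rules are consistent with that statement: the ibrutinib omission limit of more than 28 days in 8.1(f), which is not confined to adverse events, and the event-monitoring triggers in 13.3, including progression described as occurring on all three drugs. The same check is useful for Phase I, where 7.11 already ends ibrutinib at Cycle 24.

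The choice of schedule belongs to the sponsor and the investigators. The cost is protocol wording, with no new data, no added patients and no change to the statistical design.
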